5.5. Handling protocol deviations and violations

A protocol deviation/violation is defined as a failure to adhere to the protocol such as errors in applying the inclusion/exclusion criteria, the incorrect intervention being given, incorrect data being collected or measured, follow-up visits outside the visit window or missed follow-up visits. We will apply a strict definition of the ITT principle and will include all participants as per the ITT population described in section 5.3 in the analysis in some form regardless of deviation from the protocol.⁴ This includes participants who were randomised but later found to violate the inclusion or exclusion criteria. This does not include those participants who have specifically withdrawn consent for the use of their data in the first instance; however these outcomes will be explored as per other missing responses.

Where appropriate, additional sensitivity analysis for any protocol deviations and violations will be conducted for the primary outcome only. These will be described in section 9.10.

5.6. Unblinding

RATE-AF is an open label trial, blinded endpoint trial and so patients are unblinded however the investigators are blinded to the summary QoL scores at 6 and 12 months and detailed echocardiographic variables at 12 months. NTpro-BNP levels at 6 and 12 months are not known during the clinical consultation.

6. Trial population

6.1. Recruitment

A flow diagram (as recommended by CONSORT^{5, 10}) will be produced to describe the participant flow through each stage of the trial. This will include information on the number (with reasons) of losses to follow-up (drop-outs and withdrawals) over the course of the trial. A template for reporting this is given in Appendix D1.

6.2. Baseline characteristics

The trial population will be tabulated as per Appendix D2. Categorical data will be summarised by number of participants, counts and percentages. Continuous data will be summarised by the number of participants, mean and standard deviation if deemed to be normally distributed or number of participants, median and interquartile range if data appear skewed, and ranges if appropriate. Tests of statistical significance will not be undertaken, nor confidence intervals presented.⁶

7. Intervention(s)

7.1. Description of the intervention(s)

N/A.

7.2. Adherence to allocated intervention

A cross-tabulation of allocated intervention by the adherence categories stated in section 5.4 will be produced (proportions and percentages). A template for reporting adherence is given in Appendix D3.

8. Protocol deviations and violations

Frequencies and percentages by group will be tabulated for the protocol deviations and violations as per Appendix D4.

9. Analysis methods

Intervention groups will be compared using appropriate statistical models, to adjust for all covariates as specified in section 9.1, where possible. See section 9.5 - 9.10 which describes in detail for each outcome the type of analysis method to be used.

9.1. Covariate adjustment

In the first instance, intervention effects between groups for all outcomes will be adjusted for the baseline score (where appropriate), minimisation parameters (Gender, baseline EHRA) as well as age at randomisation and

baseline LVEF (as continuous variables). The minimisation variable EHRA is a categorical score with the following categories (1, 2a, 2b, 3, 4) and for minimisation, this score was categorised into (class 1, 2a) and (class 2b, 3, 4). However for the analysis we will be adjusting this variable in its original 5 categorical form.

The Bisoprolol arm will be used as a reference category for all model based analyses.

For some binary outcomes, sometimes the effect size to be estimated of interest is the relative risk rather than the odds ratio and so for these outcomes, a log-binomial model is often used. However there are convergence issues with this type of model and so if the log-binomial model fails to converge, a Poisson regression model with robust standard errors will be used to estimate the same parameters.⁷ If this also fails to converge, unadjusted estimates will be produced from the log-binomial model. It will be made clear in the final report why this occurred (e.g. not possible due to low event rate/lack of model convergence).

9.2. Distributional assumptions and outlying responses

Distributional assumptions (e.g. normality of regression residuals for continuous outcomes) will be assessed visually prior to analysis; although in the first instance the proposed primary method of estimation in this analysis plan will be followed. If responses are considered to be particularly skewed and/or distributional assumptions violated, the impact of this will be examined through sensitivity analysis; this will consist of transformation of responses prior to analysis (e.g. log transformation) in the first instance.

9.3. Handling missing data

In the first instance, analysis will be completed on received data only with every effort made to follow-up participants even after protocol violation to minimise any potential for bias. To examine the possible impact of missing data on the results, and to make sure we are complying with the intention-to-treat principle, sensitivity analysis will be performed on the primary outcome measure only.⁸ See section 9.10 for further details.

9.4. Data manipulations

The Trial Statistician will derive all responses from the raw data recorded in the database:

Age at randomisation

(Randomisation date – Date of birth) / 365.25, taking the integer part of age

SF-36 version 2

The SF-36v2 questions will be coded as follows:

- SFQ1 - Excellent=5
 Very good=4.4
 Good=3.4
 Fair=2
 Poor=1
- SFQ2 - Much better now than one year ago = 5
 Somewhat better now than one year ago = 4
 About the same as one year ago = 3
 Somewhat worse now than one year ago = 2
 Much worse now than one year ago = 1
- SFQ3a - Yes, limited a lot = 1
 Yes, limited a little = 2

No, not limited at all = 3

SFQ3b - Yes, limited a lot = 1
Yes, limited a little = 2
No, not limited at all = 3

SFQ3c - Yes, limited a lot = 1
Yes, limited a little = 2
No, not limited at all = 3

SFQ3d - Yes, limited a lot = 1
Yes, limited a little = 2
No, not limited at all = 3

SFQ3e - Yes, limited a lot = 1
Yes, limited a little = 2
No, not limited at all = 3

SFQ3f - Yes, limited a lot = 1
Yes, limited a little = 2
No, not limited at all = 3

SFQ3g - Yes, limited a lot = 1
Yes, limited a little = 2
No, not limited at all = 3

SFQ3h - Yes, limited a lot = 1
Yes, limited a little = 2
No, not limited at all = 3

SFQ3i - Yes, limited a lot = 1
Yes, limited a little = 2
No, not limited at all = 3

SFQ3j - Yes, limited a lot = 1
Yes, limited a little = 2
No, not limited at all = 3

SFQ4a - All of the time = 1
Most of the time = 2
Some of the time = 3
A little of the time = 4
None of the time = 5

SFQ4b - All of the time = 1
Most of the time = 2
Some of the time = 3
A little of the time = 4
None of the time = 5

SFQ4c - All of the time = 1
Most of the time = 2
Some of the time = 3

- A little of the time = 4
None of the time = 5
- SFQ4d - All of the time = 1
Most of the time = 2
Some of the time = 3
A little of the time = 4
None of the time = 5
- SFQ5a - All of the time = 1
Most of the time = 2
Some of the time = 3
A little of the time = 4
None of the time = 5
- SFQ5b - All of the time = 1
Most of the time = 2
Some of the time = 3
A little of the time = 4
None of the time = 5
- SFQ5c - All of the time = 1
Most of the time = 2
Some of the time = 3
A little of the time = 4
None of the time = 5
- SFQ6 - Not at all = 5
Slightly = 4
Moderately = 3
Quite a bit = 2
Extremely = 1
- SFQ7 - None = 6
Very mild = 5
Mild = 4
Moderate = 3
Severe = 2
Very severe = 1
- SFQ8 - Not at all = 5
A little bit = 4
Moderately = 3
Quite a bit = 2
Extremely = 1
- SFQ9a - All of the time = 5
Most of the time = 4
Some of the time = 3
A little of the time = 2
None of the time = 1
- SFQ9b - All of the time = 1

- Most of the time = 2
Some of the time = 3
A little of the time = 4
None of the time = 5
- SFQ9c - All of the time = 1
Most of the time = 2
Some of the time = 3
A little of the time = 4
None of the time = 5
- SFQ9d - All of the time = 5
Most of the time = 4
Some of the time = 3
A little of the time = 2
None of the time = 1
- SFQ9e - All of the time = 5
Most of the time = 4
Some of the time = 3
A little of the time = 2
None of the time = 1
- SFQ9f - All of the time = 1
Most of the time = 2
Some of the time = 3
A little of the time = 4
None of the time = 5
- SFQ9g - All of the time = 1
Most of the time = 2
Some of the time = 3
A little of the time = 4
None of the time = 5
- SFQ9h - All of the time = 5
Most of the time = 4
Some of the time = 3
A little of the time = 2
None of the time = 1
- SFQ9i - All of the time = 1
Most of the time = 2
Some of the time = 3
A little of the time = 4
None of the time = 5
- SFQ10 - All of the time = 1
Most of the time = 2
Some of the time = 3
A little of the time = 4
None of the time = 5

SFQ11a-	Definitely true = 1 Mostly true = 2 Don't know = 3 Mostly false = 4 Definitely false = 5
SFQ11b-	Definitely true = 5 Mostly true = 4 Don't know = 3 Mostly false = 2 Definitely false = 1
SFQ11c-	Definitely true = 1 Mostly true = 2 Don't know = 3 Mostly false = 4 Definitely false = 5
SFQ11d-	Definitely true = 5 Mostly true = 4 Don't know = 3 Mostly false = 2 Definitely false = 1

The following domains will be computed from the SF-36 questionnaire:

- Physical Function (PF) = SFQ3a + SFQ3b + SFQ3c + SFQ3d + SFQ3e + SFQ3f + SFQ3g + SFQ3h + SFQ3i + SFQ3j
- Physical Function Score = ((PF-10)/20)*100
- Role Limitation Due to Physical Problems (RP) = SFQ4a + SFQ4b + SFQ4c + SFQ4d
- Role Limitation Due to Physical Problems score = ((RP-4)/16)*100
- Role Limitation Due to Emotional Problems (RE) = SFQ5a + SFQ5b + SFQ5c
- Role Limitation Due to Emotional Problems Score = ((RE-3)/12)*100
- Social Functioning (SF) = SFQ6 + SFQ10
- Social Functioning Score = ((SF-2)/8)*100
- Mental Health (MH) = SFQ9b + SFQ9c + SFQ9d + SFQ9f + SFQ9h
- Mental Health Score = ((MH-5)/20)*100
- Energy/Vitality (EV) = SFQ9a + SFQ9e + SFQ9g + SFQ9i
- Energy/Vitality Score = ((EV-4)/16)*100
- Pain (P) = SFQ7 + SFQ8
- Pain Score = ((P-2)/9)*100
- General Health Perception (GHP) = SFQ1 + SFQ11a + SFQ11b + SFQ11c + SFQ11d
- General Health Perception Score = ((GHP-5)/20)*100

AGPHYSICO

$(PF*0.456) + (RP*0.362) + (Pa*0.367) + (GHP*0.199) + (EV*-0.050) + (SF*-0.028) + (RE*-0.110) + (MH*-0.256)$

AGMENTCO

$(PF*-0.227) + (RP*-0.102) + (P*-0.130) + (GHP*0.036) + (EV*0.278) + (SF*0.272) + (RE*0.329) + (MH*0.460)$

Physical Component Summary score (PCS)

$((AGPHYSICO-82.261)/20.867)*10+50$

Mental Component Summary score (MCS)

$((\text{AGMENTCO}-63.7796)/19.582)*10)+50$

EQ-5D (5 level)

The current NICE guidelines (updated October 2019) on the use of EQ-5D-5L scoring based on the most recent value set for England published by Devlin et al. 2018 was not to use this and instead to map the 5L data into 3L value set based on mapping function developed by van Hout et al. 2012.

EQ-5D-5L have developed the crosswalk value sets for the 5L to 3L and so these values will be used for scoring: (<https://euroqol.org/eq-5d-instruments/eq-5d-5l-about/valuation-standard-value-sets/crosswalk-index-value-calculator/>).

For those patients that die prior to completing the EQ5D questionnaire, for the Index score a value of "0" will be imputed since for this questionnaire, a value of 0=death.

AFEQT questionnaire overall score

$$100 - \left[\frac{(\text{sum of severity for all questions answered} - \text{number of questions answered}) * 100}{\text{Total number of questions answered} * 6} \right]$$

*Note: ignore last two questions of the AFEQT questionnaire for scoring as they will be tabulated separately

IPAQ score (as continuous score)

- Sitting = N/A for IPAQ score
- Walking = 3.3 METs
- Moderate Intensity = 4.0 METs
- Vigorous Intensity = 8.0 METs

Total MET-minutes/week: MET level x minutes of activity/day x days per week

IPAQ score= Walk (3.3*min/day*days) + Moderate (4.0*min/day*days) + Vigorous (8.0*min/day*days)

NT-pro-BNP

Since this data is expected to be not normally distributed, a log transformation (natural log) for this data will need to be done to approximate normality prior to any analysis.

Composite of diastolic indices

This outcome will be coded as a binary yes/no, with "yes" representing patients that have a diastolic dysfunction present and "no" for patients that don't.

There is an algorithm to determine whether the patient has a diastolic function or not and it will be computed based on the following:

Does the patient have any **one** of the following diastolic parameters?

- Average E/e' (taken from lateral and septal wall) ≥ 15

If yes, then Diastolic dysfunction present

If no, then 

Does the patient have **two** or more of the following diastolic parameters?

- IVRT (ms) ≤ 65 ms
- Mitral Valve E deceleration time (ms) ≤ 120 ms
- Average E/e'(taken from lateral and septal wall) ≥ 11
- Pulmonary Vein diastolic deceleration time (ms) ≤ 220

If yes, then Diastolic dysfunction present

If no, then no diastolic dysfunction present

Change in European Heart Rhythm Association (EHRA) class

This outcome will be analysed as ordinal data initially but will also be analysed as a binary yes/no variable. The original classification for this score is in an ordinal scale and the categories are 1, 2a, 2b, 3, 4 where lowest category 1 indicates best outcome and highest category 4 indicates worst outcome. For this outcome to be coded as binary we will consider any one with a change in 2 categories from worse to better as “yes” for this outcome. Comparison will be made from baseline score to 6 months and baseline score to 12 months separately. EG: if a patient had a baseline EHRA class of 3a and by 6 months they had an EHRA class of 2a then this patient will be considered as “yes” for the classification of change in EHRA class. There may be some patients that cannot achieve a 2 point improvement in the score due to the score they originally had at baseline (i.e. if someone has a baseline score of 2a or below at baseline). These patients will be classed as not improved.

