9.5. Analysis methods – primary outcome(s)

The primary outcome is the SF-36v2 physical component summary (PCS) score at 6 months.

The data for this outcome is continuous in nature and the computation for this score is described in the data manipulations section 9.4. The mean and standard deviation along with minimum and maximum values for the PCS score will be presented by treatment arm.

Data will be analysed using a linear regression model with outcome being the 6 months PCS score and independent variables in the model being the baseline PCS score, treatment arm, all minimisation variables, age at randomisation and baseline LVEF. An adjusted mean difference and 95% confidence interval will be estimated from the linear regression model and the p-value from the associated model will be produced. The Bisoprolol arm will be used as a reference category in the model and so higher values will indicate better outcome for Digoxin arm. A template for reporting the primary outcome is given in Appendix D5.

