9.6. Analysis methods – secondary outcomes

A template for reporting all the secondary outcomes is given in Appendix D6.

Patient-reported QoL

For the RATE-AF trial, questionnaires SF-36v2, EQ-5D-5L and AFEQT are administered at baseline, 6 months and 12 months.

Up-titration visits:

These questionnaires are also administered for each patient at their last up-titration visit.

Note: the data for last up-titration visit is not done at any scheduled time-point due to the fact that each patient will have different up-titration visits (i.e. some will have 6 and some may only have 1) and so for this reason the data collected for last up-titration visit will only be summarised by treatment arm and no formal analysis for this data will be conducted.

- **SF-36v2 global and domain specific scores at 6 and 12 months**

The data for these outcomes are continuous in nature and the computation for the global and domain specific scores is described in the data manipulations section 9.4. The mean and standard deviation along with minimum and maximum values for global and domain specific scores will be presented by treatment arm and time-point.

The global and domain-specific scores will be analysed separately at 6 and 12 months using the same analysis methods as described in section 9.5. for primary outcome:

- Physical component summary (PCS) score at 12 months
- Mental component summary (MCS) score at 6 months and 12 months
- Physical Function score at 6 months and 12 months

- Role Limitation Due to Physical Problems score at 6 months and 12 months
- Role Limitation Due to Emotional Problems score at 6 months and 12 months
- Social Functioning score at 6 months and 12 months
- Mental Health score at 6 months and 12 months
- Energy/Vitality score at 6 months and 12 months
- Pain score at 6 months and 12 months
- General Health Perception score at 6 months and 12 months

The range for each domain of the SF-36v2 is from 0=worst score to 100=best score. The Bisoprolol arm will again be used as a reference category for all model based analysis for SF-36v2 and so higher values will indicate better outcome for Digoxin arm.

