Appendix D6: Secondary outcomes results

SF-36v2 global and domain specific scores at 6 and 12 months

Secondary outcome	Time point	Statistic	Digoxin	Bisoprolol	Linear regression model	
					Adjusted mean difference ¹ 95% CI	P-value ¹
Physical Component Summary (PCS)						
PCS	Baseline	N Mean [SD] Min - Max			-	-
	12 months	N Mean [SD] Min - Max				
Mental Component Summary (MCS)						
MCS	Baseline	N Mean [SD] Min - Max			-	-
	6 months	N Mean [SD] Min - Max				
	12 months	N Mean [SD] Min - Max				
Physical Function Domain score (PF)						
PF	Baseline	N Mean [SD] Min - Max			-	-
	6 months	N Mean [SD] Min - Max				
	12 months	N Mean [SD] Min - Max				
Role Limitation Due to Physical Problems Domain score (RP)						
RP	Baseline	N Mean [SD] Min - Max			-	-
	6 months	N Mean [SD] Min - Max				
	12 months	N Mean [SD] Min - Max				
Role Limitation Due to Emotional Problems Domain score (RE)						
RE	Baseline	N Mean [SD] Min - Max			-	-
	6 months	N Mean [SD] Min - Max				
	12 months	N Mean [SD] Min - Max				

Social Functioning Domain score (SF)						
SF	Baseline	N Mean [SD] Min - Max			-	-
	6 months	N Mean [SD] Min - Max				
	12 months	N Mean [SD] Min - Max				
Mental Health Domain score (MH)						
MH	Baseline	N Mean [SD] Min - Max			-	-
	6 months	N Mean [SD] Min - Max				
	12 months	N Mean [SD] Min - Max				
Energy/Vitality Domain score (EV)						
EV	Baseline	N Mean [SD] Min - Max			-	-
	6 months	N Mean [SD] Min - Max				
	12 months	N Mean [SD] Min - Max				
Pain score (Pain)						
Pain	Baseline	N Mean [SD] Min - Max			-	-
	6 months	N Mean [SD] Min - Max				
	12 months	N Mean [SD] Min - Max				
General Health Perception Domain score (GHP)						
GHP	Baseline	N Mean [SD] Min - Max			-	-
	6 months	N Mean [SD] Min - Max				
	12 months	N Mean [SD] Min - Max				

1-Adjusted for treatment arm, baseline score, all minimisation variables, age at randomisation and baseline LVEF

Reference group for the treatment arm in the model is Bisoprolol arm

Higher values indicate better scores so a positive mean difference favours Digoxin arm

EQ-5D-5L summary index and visual analogue scale at 6 and 12 months

Secondary outcome	Time point	Statistic	Digoxin	Bisoprolol	Linear regression model	
					Adjusted mean difference ¹ 95% CI	P-value ¹
EQ-5D-5L summary index score[£]						
EQ-5D-5L summary index score	Baseline	N Mean [SD] Min - Max			-	-
	6 months	N Mean [SD] Min - Max				
	12 months	N Mean [SD] Min - Max				
EQ-5D-5L visual analogue scale (VAS) score[§]						

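### As written in SAP 9.4, the PCS (primary endpoint) and MCS formulas take raw item sums instead of 0-100 domain scores, so neither score can reach 50

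*SAP*

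**What the plan says.** SAP 9.4 defines each SF-36v2 domain in two steps. A symbol is first given to the sum of the item codes, for example "Pain (P) = SFQ7 + SFQ8". A separately named 0-100 quantity is then derived from it, for example "Physical Function Score = ((PF-10)/20)*100". In that second line PF can only be the raw sum, since subtracting 10 and dividing by 20 rescales a 10-30 range.

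The aggregates follow, in the bare symbols:

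- AGPHYSICO: "PF*0.456) + (RP*0.362) + (Pa*0.367) + (GHP*0.199) + (EV*-0.050) + (SF*-0.028) + (RE*-0.110) + (MH*-0.256"
- AGMENTCO, which begins "PF*-0.227) + (RP*-0.102) + (P*-0.130"

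Pain is 'Pa' in the first and 'P' in the second; only P is defined. PCS is then obtained from "AGPHYSICO-82.261)/20.867)*10+50", and MCS in the same way with centre 63.7796 and divisor 19.582.

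For the primary outcome, SAP 9.5 states that "the computation for this score is described in the data manipulations section 9.4".

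Three other places bear on intent. SAP 9.6 says "The range for each domain of the SF-36v2 is from 0=worst score to 100=best score". Appendix D6 uses the same abbreviations for the domain scores, as in "Physical Function Domain score (PF". Protocol 9.5.3 requires each instrument to be scored by its published rules.

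**The concern.** PCS at 6 months is the primary endpoint, and SAP 9.4 is the specification from which the trial statistician derives it. The centring constants, 82.261 and 63.7796, look far too large for sums of item codes that never exceed 30 per domain.

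If the formulas are coded as they stand, the primary mean difference and its confidence interval, the MCS results, and the PCS and MCS standard deviations that Appendix D7 reports for planning a future trial would all be on a compressed scale. Because the domains shrink by different factors, their relative weights would change too, so the result could not be rescued by rescaling. Conversely, a programmer who silently corrects the formula departs from the SAP, and SAP section 1 requires such departures to be described and justified.

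**Working it through.** **The plan's own figure.** The documents state no attainable range for PCS or MCS. The one design figure for the primary outcome is the sample size, and it reproduces: 2 × (1.960 + 1.036)² / 0.5² = 71.8, so 72 per arm or 144; 144 / 0.9 = 160. It is in SD units and does not depend on the PCS scale.

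**Inputs**, all from SAP 9.4 (item codes, domain sums, weights):

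| Domain | Raw min-max | Raw span / 100 | PCS weight | MCS weight |
|---|---|---|---|---|
| PF | 10-30 | 0.20 | 0.456 | -0.227 |
| RP | 4-20 | 0.16 | 0.362 | -0.102 |
| P | 2-11 | 0.09 | 0.367 | -0.130 |
| GHP | 5-25 | 0.20 | 0.199 | 0.036 |
| EV | 4-20 | 0.16 | -0.050 | 0.278 |
| SF | 2-10 | 0.08 | -0.028 | 0.272 |
| RE | 3-15 | 0.12 | -0.110 | 0.329 |
| MH | 5-25 | 0.20 | -0.256 | 0.460 |

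PCS = 10 × (AGPHYSICO − 82.261) / 20.867 + 50. MCS = 10 × (AGMENTCO − 63.7796) / 19.582 + 50. Each item enters only one domain, so the extremes below are attainable.

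**Step 1: PCS, literal reading with Pa = raw P.**
- Largest AGPHYSICO (positive weights at raw maximum, negative at raw minimum): 29.932 − 1.866 = 28.066, so PCS = 24.0.
- Smallest: 7.737 − 9.330 = −1.593, so PCS = 9.8.
- Best answer on every item: 20.602, so PCS = 20.5. Worst on every item: 5.871, so PCS = 13.4.

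**Step 2: PCS, Pa = 0-100 Pain Score, other terms raw.** AGPHYSICO runs from −2.327 to 60.729, so PCS runs from 9.5 to 39.7 (all-best 36.1, all-worst 13.0). It still cannot reach 50.

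**Step 3: MCS, literal.** Largest AGMENTCO is 25.615 − 2.938 = 22.677, so MCS = 29.0. Smallest is 5.123 − 10.280 = −5.157, so MCS = 14.8. All-best is 25.3 and all-worst 18.5.

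**Step 4: 0-100 scores throughout.** The weights sum to 0.940 (PCS) and 0.916 (MCS). All-best gives PCS = 10 × (94.0 − 82.261) / 20.867 + 50 = 55.6 and MCS = 10 × (91.6 − 63.7796) / 19.582 + 50 = 64.2. All-worst gives 10.6 and 17.4. A value of 50 is reached when all domains stand at about 87.5 (82.261 / 0.940) or 69.6 (63.7796 / 0.916). Of the two scales defined in 9.4, only this one lets both scores reach 50.

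**Step 5: size of a treatment difference.** Take a 10-point gain on the 0-100 scale in each of PF, RP, Pain and GHP:
- Intended: 10 × 1.384 / 2.0867 = 6.63 PCS points; pain contributes 0.367 / 1.384 = 27%.
- Pa = raw P: 10 × 0.22195 / 2.0867 = 1.06; pain contributes 15%.
- Pa = Pain Score: 10 × 0.55592 / 2.0867 = 2.66; pain contributes 66%.

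**Step 6: agreement with the intended score.** The documents give no domain SDs or correlations, so this step is an assumption: equal SDs and equal pairwise correlations r from 0 to 0.8.

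| r | Pa = raw P: correlation, SD ratio | Pa = Pain Score: correlation, SD ratio |
|---|---|---|
| 0 | 0.965, 0.17 | 0.736, 0.50 |
| 0.4 | 0.981, 0.16 | 0.868, 0.51 |
| 0.8 | 0.994, 0.16 | 0.962, 0.51 |

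Letting domain SDs vary between 18 and 30 widens the correlations to about 0.95-1.00 and 0.72-0.97.

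**The case against.** The strongest reply is that the intent is plain. SAP 9.6 gives 0-100 domain ranges, Appendix D6 attaches the abbreviations to domain scores, protocol 9.5.3 points to published scoring, and the constants only make sense with 0-100 inputs. On this view the text is loose notation with one workable reading, and the code may well be right. That stands as far as it goes: this is an error in the specification, and nothing in the documents shows an error in the analysis. But none of those places rewrites the formula, and Appendix D6 only makes one symbol mean two things.

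Four narrower points also have force:

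- **'Pa' is a separate slip.** The raw sums alone keep both scores below 50, and MCS does not use 'Pa'. A text-reading artefact cannot be wholly excluded for that one symbol.
- **The mixed reading is the less likely one.** A programmer who takes Pa as a 0-100 score has reason to treat the other seven terms alike. Without it, the effect on the p-value is probably modest; what remains is a mean difference, confidence interval and SDs at roughly one-sixth of their intended size.
- **Detection before the final analysis is possible.** Appendix D5 tabulates the baseline minimum and maximum, and protocol 12.3.4 plans an interim analysis. A cohort with no PCS above 24 should be noticed, but the plan does not provide for that check.
- **All-best and all-worst tests are limited.** They depend only on the sum of the weights and would miss transposed weights.

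**Conclusion.** The concern holds, and the formulas must be corrected because they define the primary endpoint. As written, PCS cannot exceed 24.0 (39.7 if Pa is taken as the Pain Score) and MCS cannot exceed 29.0. These bounds are exact and rest only on the item codes, weights and constants in SAP 9.4.

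If coded literally, the primary mean difference would be about 0.16 of its intended size for an even gain across the four physical domains (1.06 / 6.63), with altered domain weights. How far the p-value would move depends on how 'Pa' is read and on the assumed correlations, so only a range can be given.

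The sample size, the single-domain SF-36 results, EQ-5D, AFEQT, LVEF and E/e' are unaffected. Whether the published weights and constants have been transcribed correctly cannot be judged from these documents.

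**What to change.** In SAP 9.4:

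1. Write AGPHYSICO and AGMENTCO in the named 0-100 Scores (0.456 × Physical Function Score + 0.362 × Role-Physical Score + 0.367 × Pain Score, and so on).
2. Give the raw sums their own names, such as PFraw, so that each symbol has one meaning there and in Appendix D6.
3. Replace 'Pa' with the Pain Score.
4. Check the code before analysis. All-best answers should give PCS 55.6 and MCS 64.2; all-worst 10.6 and 17.4. To catch transposed weights, also run profiles with one domain at 100 and the rest at 0. PCS should then be 10.58 + 1000 × weight / 20.867, for example 32.43 for PF alone, 28.17 for Pain alone and −1.69 for MH alone. MCS should be 17.43 + 1000 × weight / 19.582, for example 5.84 for PF alone and 40.92 for MH alone.
5. Verify the weights and constants against the published scoring that protocol 9.5.3 relies on, since step 4 tests agreement with the SAP formulas only.

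The cost is a few lines of SAP text and one programming check. No change to data collection or sample size is needed.
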